Feasibility of ^1H -MRS Approach: Importantly, all of the ^1H -MRS procedures outlined above have been successfully implemented in our published preliminary studies [71, 103, 104]. These studies suggest that (1) FM patients have higher levels of Glu and Glx within the posterior insula and (2) that changes in Glu and Glx within the posterior insula are strongly correlated with improvements in pain, with reductions in clinical pain being associated with lower Glu levels. We hypothesize that our acupuncture and/or sham interventions may be directly modulating Glu and Glx within the posterior insula. However since our previous analyses combined both acupuncture and sham treated groups, we have recently tested whether acupuncture and sham acupuncture *differentially* modulate Glu levels within the insula. 19 FM patients were randomized to receive either nine manual acupuncture (MA; n=9) or nine sham (with somatosensation; n=10) treatments over the course of a month. All subjects underwent two ^1H -MRS sessions once prior to and once following treatment. Changes in Glu within the posterior insula, post-pre treatment, were significantly greater in the MA group as compared to the sham group, (mean difference in concentration post-pre treatment (s.e.m) in AIU: MA -0.82(0.32); SHAM 0.20(0.32); p=0.04). Participants receiving MA displayed slightly greater reductions in Glu within the posterior insula, suggesting that there may be subtle differences between MA and sham acupuncture with somatosensation.

Figure 6 ^1H -MRS Regions of Interest (ROIs) and Resulting Spectra from Posterior Insula Resolving Glx and GABA Signals

No differences were detected between groups for NAA, Cho, or myoInositol (all $p > 0.05$). No differences were detected between groups for any metabolites in the anterior insula (all $p > 0.10$).

9.3.3. Functional magnetic resonance imaging (fMRI) of evoked pain.

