11. STATISTICAL CONSIDERATIONS

11.1. Aim 1: At baseline, characterize altered somatosensory neurocircuitry underlying chronic pain in FM.

Hypothesis 1: Using resting fcMRI, the insula in FM patients will show more correlation with DMN, and more anti-correlation with SMN, compared to HC.

We will use dual-regression independent component analysis (ICA) to evaluate resting connectivity between DMN/SMN and insula. Two-sample t-tests will compare FM vs. HC, cluster-corrected at $p=0.05$.

Based on our previous studies, assuming DMN connectivity z score (middle insula region) of 1 for a fibromyalgia patient vs. 0.5 for a healthy control with a common standard deviation of 0.5, we will expect a typical relative effect of 1 (mean ICA-derived z score over its standard deviation). Similar effects (negative connectivity values) are expected for SMN-derived biomarkers. With the planned numbers of subjects we will have the power exceeding 97% to detect the effects by a two-sided t-test.

Hypothesis 2: Using $^1\text{H-MRS}$, FM patients will show pain related increased Glx and reduced levels of GABA within the insula and S2 as compared to HC.

Metabolite concentration from regions of interest will be assessed using spectra data input into LCModel. A two-sample T-test will compare FM vs. HC, significant at $p=0.05$.

Our sample size calculation for difference between FM and HC assumes (from pilot data) that Glx, a proxy for glutamate concentration, has mean(SD) = 10.5(1.4) in arbitrary institutional units (AIU) and a FM-HC relative difference in excess of 10%. Thus we conservatively hypothesize an average Glx around 11.5 AIU and GABA around 1.3 mmol/kg in the FM group. We conclude that we will have the power of at least 84% for the GABA and 81% for the Glx based on a two-sided t-test with unequal N (80 in FM vs. 20 in HC) at the significance level of 0.05.

Hypothesis 3: Using evoked pain fMRI, FM patients will be more sensitive to evoked pressure pain and demonstrate greater insula activation to pain stimuli, compared to HC.

A general linear model will assess brain response to experimental pain from a block design BOLD fMRI run. A group level FM - HC difference map will use a two sample t-test, cluster corrected at $p=0.05$.

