Hypothesis 2 : EA will more readily reduce Glx and increase GABA in the insula as compared to ML, which will not reduce Glx and GABA. The change in pain will correlate with change in insula GABA and Glx for EA but not ML. Glx and GABA will represent mediators for the treatment effect on change in pain.

Similar to above, linear mixed models and paired t-test analyses will evaluate, separately, Glx and GABA concentration levels taken from baseline and post-therapy H-¹MRS scans.

A reduction in the Glx of about 1.5 arbitrary institutional units (AIU) with a standard deviation not exceeding 0.6 is expected in the EA group. At the same time in the ML group a much smaller effect is expected (around 1 AIU, same standard deviation). This ensures 95% power when using a two –sided test. A similar analysis for differences in the change in GABA of 0.3 vs. 0.1 mmol/kg with a standard deviation of 0.25 gives 94% power to detect a difference.

Correlation between Glx/GABA and clinical pain (BPI) will be analyzed similar to the fcMRI biomarkers. The study has 94% power to detect correlations of 0.5 and higher.

Similar to fcMRI biomarkers, if Glx or GABA show less than 20% post-hoc power after half of the patients have been measured (correlation less than 0.18), their longitudinal measurements will be discontinued for the remaining patients.

Mediation Analysis is similar to the one proposed for connectivity.

Hypothesis 3: EA will more readily reduce pain-evoked fMRI activation in the insula as compared to ML, which will not reduce pain-evoked fMRI activation. The change in pain will correlate with change in insula response to evoked pain for EA but not ML. Insula response to evoked pain will represent a mediator for the treatment effect on change in pain.

Parameter estimates from evoked pain block-design fMRI scans will be used in a linear mixed model and post-hoc paired t-tests, similar to the approach described above.

Changes in connectivity z-score for a typical connectivity biomarker are expected to follow a different slope in EA vs. ML patients in response to pressure pain. Assuming the slope of 1.3 vs. 0.5 with the standard deviation of the pain score of approximately 1 and standard deviation of the connectivity z score at a given level of pressure pain of around 1. This ensures we will have over 94% power to detect a difference in connectivity by pressure pain slope responses with 40 patients per treatment group.

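### The 95% power for the EA–ML Glx comparison rests on an unsourced change SD of 0.6, below anything the protocol's only printed change data support, and on an ML change that conflicts with Hypothesis 2

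*Combined protocol and SAP*

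**What the plan says.** Section 11.2, Hypothesis 2, predicts that EA will lower insular Glx more "as compared to ML, which will not reduce Glx and GABA".

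The power paragraph that follows takes a mean Glx reduction of about 1.5 AIU under EA, "with a standard deviation not exceeding 0.6 is expected in the EA group". For the comparator it says that "in the ML group a much smaller effect is expected (around 1 AIU, same standard deviation"). It then concludes: "This ensures 95% power when using a two –sided test". No reference or pilot result is attached to the 0.6.

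Section 9.3.2 (feasibility of ¹H-MRS) reports the team's own longitudinal data on posterior-insula Glu in 19 fibromyalgia patients, 9 given manual acupuncture and 10 given sham needling. The post-minus-pre changes, as mean (s.e.m.) in AIU, are "MA -0.82(0.32); SHAM 0.20(0.32); p=0.04". The same section names the posterior insula as the main spectroscopy outcome. Section 11.1 describes Glx as a proxy for glutamate and gives a cross-sectional Glx SD of 1.4 AIU. No SD for a change in Glx is reported anywhere.

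**The concern.** For a stated difference and sample size, power depends entirely on the SD of the within-patient change. Here that SD is worded as an upper bound, yet the one data set in the protocol that speaks to it suggests a considerably larger value. If the larger value is nearer the truth, a null EA–ML result read against a 95% claim would be taken as strong evidence of no difference, when roughly four such trials in ten would miss the planned 0.5 AIU.

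The second problem needs no pilot data. The hypothesis gives ML no Glx reduction, while the power calculation gives it about 1 AIU. The assumed ML change sets the EA–ML difference, so the plan does not have one settled effect size to be powered for.

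**Working it through.** **Inputs.** EA reduction 1.5 AIU, ML reduction 1 AIU, common SD 0.6 (section 11.2); 40 per arm (synopsis); two-sided test (section 11.2). The 5% level is not repeated in this paragraph; it is carried over from the Aim 1 calculation, "at the significance level of 0.05". No dropout is allowed for.

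**Step 1: reproduce the plan's figure.** Two-sample t-test on change, n = 40 per arm, 78 df. Noncentrality = δ / (σ√(2/n)) = 0.5 / (0.6 × √(2/40)) = 0.5 / (0.6 × 0.2236) = 3.73. Power = 95.7% (96.1% by the normal approximation). This matches the stated 95%.

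**Step 2: the SD implied by the pilot.** SD = s.e.m. × √n.
- Manual acupuncture: 0.32 × √9 = 0.96.
- Sham: 0.32 × √10 = 1.01.
- Pooled: √[(8 × 0.96² + 9 × 1.01²) / 17] = 0.988 on 17 df.

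Check that 0.32 really is a standard error: the difference is 0.20 − (−0.82) = 1.02; its standard error is √(0.32² + 0.32²) = 0.4525; t = 2.25 on 17 df, p = 0.038, agreeing with the printed 0.04. Were 0.32 an SD, p would be about 2 × 10⁻⁶.

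95% interval for the SD: 0.988 × √(17/30.19) = 0.74 to 0.988 × √(17/7.564) = 1.48. It excludes 0.6.

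**Step 3: power for 0.5 AIU, and the detectable difference.** At 40 per arm the difference detectable with 80% power is 0.634 × SD.

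| Change SD (AIU) | Noncentrality, δ = 0.5 | Power, δ = 0.5 | Difference for 80% power (AIU) |
|---|---|---|---|
| 0.6 (plan) | 3.73 | 96% | 0.38 |
| 0.74 (lower limit) | 3.02 | 85% | 0.47 |
| 0.8 | 2.80 | 79% | 0.51 |
| 0.988 (pilot) | 2.26 | 61% | 0.63 |
| 1.2 | 1.86 | 45% | 0.76 |
| 1.48 (upper limit) | 1.51 | 32% | 0.94 |

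Rounding of the s.e.m. (0.315 to 0.325) moves the pilot row only between 62% and 60%. With 36 evaluable per arm (an assumption), it would be about 56%.

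**Step 4: effect of the ML assumption.** If ML is assumed not to change Glx and EA stays at 1.5 AIU, the difference is 1.5 AIU. Power is then above 99.9% at SD 0.988 and 99.4% at SD 1.48. If ML falls by 1 AIU as assumed, a paired test within ML (n = 40) is significant with power above 99.9% at SD 0.6 or 0.99.

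**Cross-check.** If the cross-sectional SD of 1.4 applied at both visits (an assumption), the pre-post correlation needed is 1 − SD²/(2 × 1.4²): 1 − 0.36/3.92 = 0.91 for a change SD of 0.6, and 1 − 0.98/3.92 = 0.75 for 0.99.

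**The case against.** The sum itself is correct, so this is a question about an input and not an arithmetic error.

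The pilot is also an imperfect guide. It measured Glu; Glx adds glutamine, and the documents give neither the variance of glutamine change nor its covariance with Glu. It used manual needling and a sham with somatosensation, nine sessions, and only 19 patients. The background section describes earlier longitudinal Glx work by the same team that is not reproduced here, and 0.6 may come from it. A reader might therefore infer that the pilot contradicts 0.6, or that the true power is 61%. The documents support neither: they show an unsourced bound that lies below the whole interval from the only printed change SD. That much stands, because the pilot is on the AIU scale, in the region named as the main outcome, for a metabolite the plan treats as closely linked to Glx.

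It can also be said that the pilot's own difference of 1.02 AIU would give 99.5% power at SD 0.988. That is true, but the plan states 0.5 AIU, so it does not rescue the 95%.

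Finally, a reader might infer that a significant fall within ML would refute Hypothesis 2. It would contradict only the clause that ML leaves Glx unreduced; the claim that EA lowers Glx more than ML would be untouched.

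**Conclusion.** The point holds as an unsupported power assumption together with an internal inconsistency. For the stated 0.5 AIU difference, the 95% requires a change SD no larger than about 0.61. The only change SD available from the documents is about 0.99, which gives about 61% as a central value within a range of 32% to 85%. This assumes that Glu change variability carries over to Glx under EA and ML, approximate normality, a two-sided 5% level and 40 evaluable patients per arm.

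It does not follow that the comparison is underpowered. That depends on which ML change is meant: at 0.5 AIU the 95% is not supported, whereas at 1.5 AIU power exceeds 99% over the whole pilot interval. The conflict between the hypothesis and the assumed ML reduction is plain from the text and has to be settled first.

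**What to change.** In section 11.2, Hypothesis 2:

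1. Reconcile the assumed ML change with the hypothesis and state the EA–ML difference that results.
2. Replace the single 95% with power, or the detectable difference, over change SDs from 0.6 to about 1.5, including the pilot value of 0.99. Alternatively, cite Glx change data that justify 0.6.
3. If 0.5 AIU is kept without such data, state about 61% (32% to 85%), with 0.63 AIU detectable at 80% power, and note that the SD comes from Glu. If the ML change is set near zero, state the 1.5 AIU difference; power then exceeds 99% throughout the pilot interval.
4. State the significance level and the number of evaluable patients assumed.

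This is wording only, with no change to design, sample size or procedures. The price is a less favourable printed figure if 0.5 AIU remains the target.

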 - **Hypothesis 3:** EA will more readily reduce pain-evoked fMRI activation in the insula as compared to ML, which will not reduce pain-evoked fMRI activation. The change in pain will correlate with change in insula response to evoked pain for EA but not ML.
- ◆ **Aim 3. Evaluate the ability of altered neurocircuitry at baseline to predict clinical response to electro- and mock laser acupuncture**
- **Hypothesis 1:** FM patients with greater baseline DMN-insula positive correlation and SMN-insula anti-correlation will display greater clinical response to EA. There will be no predictive value for ML – which is an inert form of sham acupuncture with no somatosensory afference.
 - **Hypothesis 2:** FM patients with greater baseline insular Glx/GABA ratios will display greater clinical response to EA. There will be no predictive value for ML.
 - **Hypothesis 3:** FM patients with greater baseline pain-evoked insular activation will display greater clinical response to EA. There will again be no predictive value for ML.

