8. PATIENT SELECTION AND ENROLLMENT

8.1. Patient Eligibility

8.1.1. Inclusion Criteria

Inclusion Criteria for Fibromyalgia Participants

- Must have self-reported FM symptoms for at least one year and also meet the newly proposed Wolfe et al 2011 criteria for FM. Continued presence of pain more than 50% of days.
- Pain greater than or equal to 4 on a 10cm Visual Analog Scale (VAS) for pain; 7-day recall; [Note: The VAS is widely used in clinical pain research and as such we chose to use it for inclusion criteria and for clinical pain assessment below. Within our group numerical ratings scales 0-100 are more commonly used in quantitative sensory assessment, and as such we chose to use NRS scales for evoked pain assessments below.]
- Willing to limit the introduction of any new medications or treatment modalities for control of FM symptoms during the study.
- Able to travel to the study site to receive acupuncture treatments up to two times weekly.
- Over 18 and under 65 years of age.
- Right-handed.
- Female.
- Capable of giving written informed consent.

Inclusion Criteria for Healthy Control Participants

- Over 18 and under 65 years of age.
- Female.
- Right-handed.
- Pain equals 0 on a 10cm Visual Analog Scale (VAS) for pain; 7-day recall
- Willing to complete all study procedures.
- Capable of giving written informed consent.

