Seed-voxel Functional Connectivity Approach: For exploratory analyses, we will also use a complementary approach to evaluate intrinsic connectivity involving seed-voxels from distinct brain regions (see below). The average timeseries from these regions is used as a regressor in a whole brain GLM to find which other regions contain correlated timeseries. While this approach can yield more focused inferences, there is some bias in choice of exact seed location and contour [99]. Thus seeds will be carefully chosen based on the results of the evoked pain fMRI scan, with particular focus on insular clusters.

Feasibility of BOLD Approach: Importantly, a similar approach has been successfully implemented in our previous studies [10, 59, 60]. One such study contrast resting connectivity in 18 FM patients and 18 HCs, and evaluated the relationship of intrinsic connectivity to spontaneous clinical pain [48]. We found that FM patients had greater connectivity between the DMN and insula as well as S2 (**Figure 4**) – brain regions known to process evoked experimental pain. Furthermore, greater spontaneous pain at the time of the scan correlated with greater intrinsic connectivity between the insula and DMN. Our most recent publication showed that a longitudinal course of manual or sham acupuncture (with somatosensation) was able to decrease DMN-insula connectivity [59].

We also have pilot fMRI data from N=18 chronic low back pain (cLBP) patients. Resting fMRI data were collected before and after provocation of patients own clinical pain with specific maneuvers, similar to our recent published study [99]. In addition to replicating again our finding that DMN-insula connectivity is correlated with increasing spontaneous clinical pain, we also noted that higher clinical pain, both before and after maneuvers, was correlated with more pronounced anti-correlation between anterior insula and SMN (**Figure 5**). Moreover, the after-before maneuver increase in pain was negatively correlated with change in SMN connectivity to the left anterior insula. These results support our hypotheses for increased anti-correlation between SMN and insula in chronic pain (here FM) patients, and its relationship to clinical pain.

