9.4.1. Screening

- Informed Consent review and documentation
- Review study procedures and requirements with the patient
- Collect demographic and sociodemographic information
- Record tender point count
- Complete 7-day recall VAS pain scales
- Conduct psychological screening interviews (HADS and PHQ-9). Confirm that the patient is not experiencing active suicidal ideation or intent. Any participant experiencing active suicidal ideation will be directed to seek medical help.
- Obtain medical history and fibromyalgia treatment history (*FM cohort only*)
- Conduct a physical assessment (height and weight) and confirm and document results of the Wolfe et al 2011 criteria for FM .
- Urine pregnancy test for women of childbearing potential
- Document current concomitant medications

- Collect:
 - Brief Pain Inventory - Severity and Interference scales [BPI]
 - FM Survey Questionnaire [FSQ]
 - Fibromyalgia Impact Questionnaire [FIQ-R] (*FM cohort only*)
- The Screening visit and Baseline Behavioural visit may occur on the same day.

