Change in pain-evoked fMRI activation will be correlated with the change in clinical pain. To do this evoked pain responses will be added as covariates into the linear mixed model regressing BPI pain on other covariates.

Mediation Analysis is similar to the one proposed for connectivity.

11.3. Aim 3: Evaluate the ability of altered neurocircuitry at baseline to predict clinical response.

This aim evaluates a *predictive* value of the neuroimaging biomarkers by studying whether their measurements at baseline correlate with pain responses to treatments.

Hypothesis 1: Greater baseline DMN-insula/S2 connectivity and SMN-insula/S2 anti-correlation, will display greater clinical response to EA vs. ML

We will use baseline estimates of DMN and SMN connectivity, taken from the dual regression ICA analysis, as independent variable in a multiple regression model with dependent variable set as the change score (post-therapy – baseline) for clinical pain (Brief Pain Inventory; BPI). Regression slopes will be contrast between different pairs (e.g. EA vs. ML) set in the same regression model. We will explore within-group correlations for individual therapies if the difference map for any two therapies is significant, at cluster corrected $p=0.05$.

Hypothesis 2: FM patients with greater baseline insular and S2 Glx/GABA ratios will display greater clinical response to EA as compared to ML.

An identical approach will be used as for hypothesis 1 above, but with Glx/GABA ratio as dependent variable.

Hypothesis 3: FM patients with greater baseline pain-evoked insular activation will display greater clinical response to EA as compared to ML.

An ROI analysis will determine baseline insula response to evoked pain. This parameter estimate will then be used as a dependent variable in an identical multiple linear regression approach, as detailed above.

Power. The expectations for correlations between the baseline measurements of biomarkers and clinical pain responses are set similar to the mechanistic setting. We expect to uncover correlations of 0.5 between measurements at baseline and the change in pain in response to treatment (mainly in the EA arm). We will have 94% power to detect such correlations.

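### Aim 3 omits baseline BPI from its pain-change model: the EA-vs-ML slope contrast is noisier than it need be, and within-arm correlations can be distorted towards the hypothesis

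*Combined protocol and SAP*

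**What the plan says.** Section 11.3, Hypothesis 1, takes the baseline DMN and SMN connectivity estimates "as independent variable in a multiple regression model with dependent variable set as the change score", post-therapy minus baseline, in clinical pain measured by the BPI. The comparison of arms is built into that model: "Regression slopes will be contrast between different pairs (e.g. EA vs. ML) set in the same regression model". Correlations inside an arm come second: "We will explore within-group correlations for individual therapies if the difference map for any two therapies is significant". Hypotheses 2 and 3 are to use an identical approach (they call the biomarker the dependent variable, which I read as a slip). No baseline-pain covariate is named in 11.3, in the evoked-pain analysis of 9.3.3, or in the synopsis.

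Section 9.3.1 reports from the team's earlier fibromyalgia data that "greater spontaneous pain at the time of the scan correlated with greater intrinsic connectivity between the insula and DMN". Section 9.3 says more generally that the imaging measures vary with the patient's pain state. Section 5 makes a statement about the sham arm alone: "There will be no predictive value for ML". The only power figure for Aim 3 is 94% for a correlation of 0.5, mainly in the EA arm.

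The schedule in section 3.1 collects BPI at screening, at the baseline behavioural session (V1) and at the baseline MRI (V2). The plan does not say which of these is the baseline in the change score.

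**The concern.** Baseline pain is one term of the outcome, and the regressor is, on the plan's own account, a correlate of pain. If a patient's pain is temporarily high at baseline and the biomarker is high with it, her pain will tend to fall without any treatment. The biomarker then appears to predict improvement.

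Entry favours temporary highs, since patients need "Pain greater than or equal to 4 on a 10cm Visual Analog Scale (VAS) for pain; 7-day recall", and "The Screening visit and Baseline Behavioural visit may occur on the same day". The spurious association has the sign that Aim 3 predicts: higher biomarker, larger fall in pain. It would arise equally in both randomised arms. It could therefore inflate the EA correlation and also make ML seem predictable, against the claim in section 5.

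Separately, leaving out a covariate that is strongly related to the outcome costs precision in the slope contrast, which is the test that carries the Aim 3 conclusion.

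**Working it through.** **The plan's own figure.** For r=0.5, n=40 and two-sided 0.05 (sidedness is not stated for Aim 3, so I assume it as in Aims 1 and 2), the noncentrality is 0.5/sqrt(0.75) x sqrt(40) = 3.65 on 38 df. Power is 94.5%; the Fisher z approximation gives 91.6%. The stated 94% is thus reproduced as a one-arm correlation test. For the contrast of r=0.5 in EA with r=0 in ML, Fisher z gives 0.549/sqrt(2/37) = 2.36, and power of about 66%.

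**Within-arm correlation when nothing is predicted.** Let r be the biomarker's correlation with baseline pain, r1 its correlation with follow-up pain, and rho the baseline-to-follow-up correlation of pain. With equal pain variances:

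corr(biomarker, change) = (r1 - r)/sqrt(2(1 - rho)).

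The documents give none of these values. I assume r from 0.3 to 0.5 and rho from 0.4 to 0.8, and consider three cases.

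- Biomarker tracks only stable pain (r1 = r): the correlation is 0 and the false-positive rate is 5%.
- Biomarker follows current pain (r1 = r x rho): the correlation is -r x sqrt((1 - rho)/2), tabulated below.
- Biomarker reflects only transient pain (r1 = 0): -0.30 to -0.79 for rho from 0.5 to 0.8.

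Current-pain case (rejection rate at n=40 by Fisher z, two-sided 0.05; the critical |r| is 0.312):

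| r | rho | Null correlation | Significant at n=40 |
|---|---|---|---|
| 0.3 | 0.4 | -0.16 | 17% |
| 0.3 | 0.6 | -0.13 | 13% |
| 0.3 | 0.8 | -0.09 | 9% |
| 0.5 | 0.4 | -0.27 | 40% |
| 0.5 | 0.6 | -0.22 | 28% |
| 0.5 | 0.8 | -0.16 | 16% |

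**The slope contrast under the null.** With an additive treatment effect, the artefact has the same expected slope in both arms and cancels. Simulated trials of 40 per arm gave a false-positive rate of about 5% in all three cases, with and without baseline BPI as a main effect.

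**Precision of the slope contrast.** Before conditioning on the biomarker, the outcome variance is 2(1 - rho) unadjusted and 1 - rho^2 adjusted. The ratio is (1 + rho)/2, or 0.7, 0.8 and 0.9 at rho = 0.4, 0.6 and 0.8. I simulated 20,000 trials per setting with r=0.5, the current-pain case, and an EA-only slope of 0.5 SD of pain per SD of biomarker:

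| rho | Power unadjusted | Power with baseline BPI |
|---|---|---|
| 0.4 | 54% | 64% |
| 0.6 | 69% | 76% |
| 0.8 | 92% | 94% |

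Power also rose or held in the stable and transient cases, and at r=0.3.

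**What adjustment does inside one arm.** At r=0.5 and rho=0.6, adding baseline BPI changes the false-positive rate within ML as follows:

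| Case | Unadjusted | Adjusted |
|---|---|---|
| Stable pain | 5% | 44% |
| Current pain | 28% | 5% |
| Transient pain | 97% | 80% |

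In the stable case the induced partial correlation is (0.5 - 0.3)/sqrt(0.75 x 0.64) = +0.29, opposite in sign to the hypothesis.

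**The case against.** The strongest reply is that the plan already protects its main conclusion. The test is the EA-vs-ML contrast, where the artefact cancels. Within-arm correlations are explored only after a significant between-therapy difference, and 11.3 sets no separate test of ML. The predictive interim look is to be treated informally. All of this stands. A reader might infer that regression to the mean alone would make the biomarkers appear to predict response and so undermine Aim 3. The documents do not support that: the planned contrast is unbiased under an additive effect, and the artefact needs a biomarker that shares the temporary part of baseline BPI.

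The inputs are also assumed. Section 9.3.1 gives no coefficient, and the plan's 0.5 is a target correlation for the EA arm, not a cross-sectional baseline correlation. Tracking of pain at the scan is documented in fibromyalgia for DMN-insula connectivity, against spontaneous pain rather than BPI. The SMN evidence comes from low back pain pilot data, and evoked activation has only the general sentence in 9.3. This limits how firmly any size can be stated.

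Finally, compulsory adjustment inside each arm is not a cure: it can create bias if the biomarker tracks stable pain. Nor does it sharpen the within-arm slope. At r=0.5 and rho=0.6 in the current-pain case, the slope variance is proportional to 0.64/0.75 = 0.85 adjusted against 0.76 unadjusted. This too stands, and it is why the remedy below treats the contrast and the within-arm correlations differently.

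What the reply leaves untouched is the loss of precision in the contrast. The gate decides when within-arm correlations are examined, but does not remove distortion from those then reported. Section 9.3.3 also plans to correlate baseline activation with pain change and states no contrast or gate there.

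**Conclusion.** The omission is real and worth correcting, but it does not invalidate the Aim 3 test. In the slope contrast it costs power: about 10 percentage points at rho=0.4, 7 at rho=0.6 and 2 at rho=0.8, under the assumed r=0.5 and EA-only slope. The gain is useful because the stated 94% refers to one arm, while the contrast has about 66% power on the plan's own 0.5 against zero.

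Within an arm, a biomarker with no predictive value could show a correlation of about -0.09 to -0.27 with pain change and reach significance 9% to 40% of the time, if it follows current pain and r and rho lie in the assumed ranges. The figure is zero for a purely stable correlate and larger for a purely transient one. A correlation in ML would therefore not by itself refute the claim of no predictive value, and one in EA would not by itself establish prediction.

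One limit applies to the contrast. If EA reduces pain proportionally (assumed 35%, baseline mean 5.5, SD 1.5, r=0.5, rho=0.6), its false-positive rate in the stable, current and transient cases is 14%, 8% and 5% unadjusted, and 21%, 10% and 5% with a baseline main effect. Adding a baseline-by-treatment term gives 9%, 5% and 13%. That is a matter of the scale of the treatment effect, not regression to the mean, and neither form of adjustment removes it in every case.

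**What to change.** In section 11.3:

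1. State which pre-randomisation BPI (screening, V1 or V2) and which BPI score is the baseline.
2. Add that value as a main-effect covariate in the change-score regression that tests the EA-vs-ML slope contrast, for all three hypotheses.
3. State that claims of prediction rest on that contrast.
4. Report within-arm correlations, including those for evoked activation in 9.3.3, both unadjusted and adjusted for baseline BPI. Label them exploratory, because neither version is unbiased under every model.

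A sensitivity analysis with a baseline-by-treatment term would show whether the contrast depends on an additive effect.

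The cost is one degree of freedom in the main model, a few sentences and slightly more reporting. No new data are needed.
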